1.3 Relevant Scientific Background

Over the past decade, researchers have explored new pathophysiological theories, proposing a connection between BPPV and oxidative stress, which triggers an inflammatory process explainable by ultrastructural mechanisms. Walther et al. demonstrated that human otoconia can exhibit varying degrees of ultrastructural degeneration, from minor to extensive changes.² Severe morphological alterations can manifest as fractures with substantial loss of calcium-rich otoconial material. High-grade disintegration of otoconia leads to complete dissolution and fragmentation of calcium-rich material into the endolymph, potentially causing BPPV symptoms. Calcium metabolism and oxidative stress, intertwined processes, closely involve inflammation. The endoplasmic reticulum, a primary calcium storage organelle, can increase calcium influx under stress, triggering a cascade of reactive oxygen species (ROS) formation in mitochondria.³

Further supporting this, Güçlütürk et al. investigated the potential role of inflammation in BPPV by studying the levels of IL-1 β , IL-6, and TNF- α .⁴ These pro-inflammatory mediators were significantly higher in BPPV patients and decreased with routine Brandt-Daroff repositioning maneuvers performed over 14 days. This suggests a possible inflammatory component in BPPV pathogenesis. Whether it is oxidative stress, otolith formation, migration into the semicircular canals, or the vertigo attacks in BPPV, a primary increase in inflammatory mediators can result.

These novel findings, elucidating the crucial role of inflammation in BPPV pathophysiology, offer new avenues for pharmacological treatment. Conventional medications like betahistine or flunarizine, often prescribed for BPPV, primarily offer symptomatic relief without addressing the underlying cause. Furthermore, not all patients are amenable to routine maneuver therapy, such as the Brandt-Daroff maneuver, a definitive BPPV treatment proven to reduce pro-inflammatory mediators when performed consistently for 14 days.⁴

In recent years, particularly since the COVID-19 pandemic, Traditional Indonesian Modern Medicines, or Obat Modern Asli Indonesia (OMAI)—natural and indigenous Indonesian drugs with scientific evidence of safety and efficacy—have seen rapid development.⁵ Among OMAI with potential for BPPV pharmacotherapy are *Ginkgo biloba* and oral lumbrokinase DLBS1033, which contains *Lumbricus rubellus* or earthworm extract. The oral lumbrokinase DLBS1033 exhibits pleiotropic effects, effectively inhibiting the expression of inflammatory mediators implicated in BPPV pathophysiology, including NF- κ B, TNF- α , and VCAM-1.⁶

1.4 Informed Consent

The study includes a detailed Informed Consent form (attached in this document), which outlines essential information for prospective participants, including the research title, type, researchers' names and addresses, research location (Neurology Polyclinic and Clinical Pathology Laboratory of [name] General Hospital Surakarta), study objectives, procedures (interviews, physical examination, blood sampling for biomarkers), participant selection criteria, voluntary participation, confidentiality, benefits (free blood sampling and biomarker analysis, access to results, transportation allowance of IDR 100,000 per visit for blood examination), and potential risks (pain at the blood sampling site).

2. STATISTICAL ANALYSIS PLAN (SAP)

2.1 Data Analysis

Statistical analysis was performed using SPSS for Windows version 25.0.

2.2 Specific Statistical Methods

- Normality test: The Kolmogorov-Smirnov test was used to check the normality of the data distribution for all variables. The Kolmogorov-Smirnov test was performed to verify the assumption of normal distribution for all variables, confirming that the data met this critical assumption for the subsequent parametric tests.
- Comparison between groups (day 7 and day 14):
 - Independent T-test: This test was used to determine significant differences between the oral lumbrokinase DLBS1033 group and the betahistine group for:
 - Mean DHI scores,
 - Mean VSS-SF scores,
 - Mean TNF- α levels,
 - Mean IL-1 β levels,
 - Mean VCAM-1 levels.
- Analysis of symptom improvement time (multiple repeated ANOVA):
 - Given the significant statistical differences found with the independent T-test, further analysis regarding the time to symptom improvement in BPPV patients receiving oral lumbrokinase DLBS1033 was performed using multiple repeated ANOVA.
- Post-hoc analysis: Tukey B post-hoc test was used to compare the mean scores/levels between groups.

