- Sample size: The minimum sample size was calculated using Sopiyudin's sample size¹ formula with a 95% confidence interval (CI) and 5% confidence limits. Based on a total population of 751 peripheral vertigo patients treated at the neurology polyclinic of [name] in the last year, the calculation resulted in a minimum sample of 40 patients. An additional 10% was added to anticipate dropouts, making the total sample size 44 patients.
- Variable identification:
 - Independent variable: BPPV therapy.
 - Dependent variables: inflammation level, quality of life, time to improvement of dizziness symptoms in BPPV patients.
 - Confounding variables: age, body mass index, gender.
- Operational definition of research variables:
 - BPPV therapy: Administration of oral lumbrokinase (DLBS 1033, 2x490 mg daily) or betahistine (2x12 mg daily) for 14 days to diagnosed BPPV patients.
- Research instruments: Dizziness Handicap Inventory (DHI) and Vertigo Symptom Scale Short Form (VSS-SF) questionnaires, and biomarker examination (IL-1 β , TNF- α , VCAM-1) using Human Quantikine R&D Systems kits on a Thermo Fisher Invitrogen auto-analyzer according to manufacturer specifications.
- Randomization protocol: The study protocol involved a two-block randomization to ensure balanced group assignments. The random sequences for the group allocation were generated by independent personnel of the direct study management and kept in sealed

envelopes. This allocation concealment ensured that neither the investigator team nor the participants knew their assigned treatment. Each package was coded with the subject identification number according to the generated random number and assigned to each eligible subject. These codes remained unrevealed until the study's completion.

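### A Kolmogorov-Smirnov test at about 22 per arm is taken to confirm normality, and the biomarkers get only raw-scale t-tests whatever it shows; if levels are skewed, power is lost

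*Combined protocol and SAP*

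**What the plan says.** SAP section 2.2 opens with the normality check: "The Kolmogorov-Smirnov test was used to check the normality of the data distribution for all variables". It reports the outcome as "confirming that the data met this critical assumption for the subsequent parametric tests". The between-group analysis at days 7 and 14 follows: "Independent T-test: This test was used to determine significant differences between" the two arms on five mean values, the last of them "Mean VCAM-1 levels". No transformation, rank test, baseline covariate or alternative method is given.

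The SAP does not say whether the K-S test used the Lilliefors correction (needed when the mean and SD are estimated from the same data), what significance level it used, or whether it was run per arm or on pooled data.

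Protocol section 1.2 sets the size: "the calculation resulted in a minimum sample of 40 patients", then an allowance for dropout, "making the total sample size 44 patients". Allocation is meant to be balanced, so about 22 per arm.

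**The concern.** A non-significant goodness-of-fit test shows only that the sample did not contradict normality. At 22 per arm that is weak evidence, yet the SAP uses it as the justification for its parametric tests. The check also leads nowhere, because the t-tests are the only between-group method listed whatever it shows.

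Three of the five objectives in protocol section 1.1 are biomarker comparisons. Concentrations cannot fall below zero, so right skew is plausible enough to plan for. If it is present and the treatment effect is proportional, a raw-scale t-test wastes power. The sample-size paragraph states no power, effect size or SD, so nothing shows a margin to absorb such a loss.

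**Working it through.** **Inputs from the documents.** Total 44, balanced arms: 44 / 2 = 22 per arm, or 40 / 2 = 20 after the planned dropout. The step from 40 to 44 reproduces as 40 × 1.10. The 40 itself does not follow from the stated inputs: the usual finite-population precision formula with N = 751, limits of 0.05, z = 1.96 and p = 0.5 gives 751 × 0.25 × 3.8416 / (0.0025 × 750 + 3.8416 × 0.25) ≈ 254. That is a separate matter; 22 per arm is taken here as planned.

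**Assumptions.** The documents give no SD, skewness or assay limit, and no alpha for the t-tests. I assume log-normal levels, a multiplicative effect, two-sided alpha 0.05, and a range of log-SD σ.

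**Step 1: the effect.** With 22 per arm, a t-test on the log scale has 80% power at a standardised difference of 0.8646. The matching geometric mean ratio is exp(−0.8646 σ).

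**Step 2: power on the raw scale** (simulation, 40,000 to 100,000 runs; repeat runs agree to about 1.5 points).

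| σ | Ratio | Log t-test | Raw t-test | Loss, points | Raw type I error |
|---|---|---|---|---|---|
| 0.3 | 0.77 | 80% | 78% | 2 | 0.05 |
| 0.5 | 0.65 | 80% | 75% | 5 | 0.048 |
| 0.8 | 0.50 | 80% | 68% | 12–13 | 0.044 |
| 1.0 | 0.42 | 80% | 61–62% | 18–19 | 0.039 |

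At 20 per arm the results are almost the same. A rank-sum test has about 78% throughout.

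**Step 3: would K-S reveal the skew?** At the 5% level the critical distance for n = 22 is 0.290 for the plain test (1.358 / √22) and about 0.184 for Lilliefors.

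| | σ = 0.5 | σ = 0.8 | σ = 1.0 |
|---|---|---|---|
| Plain, one arm rejected | 1% | 9% | 20% |
| Plain, both arms pass | 97% | 82% | 64% |
| Raw v log power in those that pass | 76 v 80% | 72 v 80% | 72–73 v 81% |
| Lilliefors, one arm rejected | 38% | 69% | 83% |
| Lilliefors, both arms pass | 39% | 10% | 3% |
| Raw v log power in those that pass | 81 v 81–82% | 84 v 83% | 86–88 v 83–84% |
| Plain, pooled 44 rejected (effect present) | 10–11% | 51–55% | 78–80% |
| Lilliefors, pooled 44 rejected (effect present) | 72% | 97% | over 99% |

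The plain per-arm test therefore usually misses the skew, and the loss among datasets that pass is about 4 points at σ = 0.5 and 8 to 9 at 0.8 and 1.0. Lilliefors leaves essentially no loss among those that pass. Those few datasets are a selected set, in which the raw test's conditional type I error is about 0.06, 0.09 and 0.11. Pooled plain testing detects the skew about half the time at 0.8 and about four times in five at 1.0.

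**Step 4: the cost of the log scale if the data are normal.** With normal data, a coefficient of variation of 0.2 to 0.3 in the reference arm and 80% power on the raw scale, the log t-test has about 75% to 79%. That is a loss of about 1 to 5 points.

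**The case against.** The strongest reply has four parts.

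- **Skewness is not shown.** This stands. The documents give no distribution, the exclusion criteria remove several conditions that could produce high values, and at σ = 0.3 the loss is under 2 points. The case is for planning against skew; it does not show that skew is present.
- **The K-S test may work.** A reader might infer that skewed biomarkers passed the check unnoticed. The documents do not support that, because it holds only for the plain per-arm test and the SAP does not say which version was used. A reader might also infer that pooled variables were tested instead of within-arm residuals; the text does not settle that either. What remains is that a failed test would leave the analyst with no planned method.
- **The raw scale may be the target.** A difference in arithmetic means is a legitimate quantity, and the objectives speak of decreases, which can take either sign. The SAP should then name that target as its reason, instead of resting on a normality test.
- **The data are in.** Section 2.2 is in the past tense and reports significant t-test differences, without saying for which outcomes. Prospective power has less force then, and replacing the analysis silently would be a post-data change. This limits how the fix is presented; it does not rescue the confirmation claim.

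**Conclusion.** The point holds in a limited form. The claim that K-S confirmed normality is unsupported at this sample size, and that needs no assumption about the data. The absence of any planned alternative is plain from section 2.2.

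The power loss is conditional on log-normal levels and a multiplicative effect: about 2, 5, 12–13 and 18–19 points at log-SD 0.3, 0.5, 0.8 and 1.0 when the t-test is run regardless of the check.

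A reader might go further and conclude that the t-tests give too many false positives, or that the reported significant differences are unsound. Neither follows: the unconditional type I error is 0.05 or lower at every log-SD examined. The issue is efficiency and justification.

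**What to change.** - Delete the statement that K-S confirms normality, and do not let a normality test choose the method. Report which version was used, at what level, and whether per arm or pooled.
- Analyse IL-1β, TNF-α and VCAM-1 by ANCOVA on the log scale with log baseline as covariate. The objectives on decreases imply that baseline levels exist. Report geometric mean ratios with 95% CIs and judge fit from residual plots.
- Give a Wilcoxon rank-sum test as sensitivity analysis. DHI and VSS-SF can stay on their original scale.
- Because the text indicates that data were already analysed, label these analyses as added later and show them beside the original t-tests.

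The cost is a few lines of SAP text and code. Effects will read as ratios, and about 1 to 5 points of power are lost if the data are in fact normal. Baseline adjustment brings its own gain (log-scale power of about 0.82–0.83, 0.89–0.90 and 0.97 at assumed baseline correlations of 0.3, 0.5 and 0.7), which should not be credited to the log scale.

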1. STUDY PROTOCOL

1.1 Objectives

The research aims to determine the differences in:

- Decrease in IL-1 β levels between benign paroxysmal positional vertigo (BPPV) patients receiving oral lumbrokinase DLBS1033 therapy and those receiving betahistine therapy.
- Decrease in TNF- α levels between BPPV patients receiving oral lumbrokinase DLBS1033 therapy and those receiving betahistine therapy.
- Decrease in VCAM-1 levels between BPPV patients receiving oral lumbrokinase DLBS1033 therapy and those receiving betahistine therapy.
- Quality of life between BPPV patients receiving oral lumbrokinase DLBS1033 therapy and those receiving betahistine therapy.
- Time to improvement of dizziness symptoms between BPPV patients receiving oral lumbrokinase DLBS1033 therapy and those receiving betahistine therapy.

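### Between-arm t-tests on five outcomes at two days, with no primary comparison, significance level or adjustment, give roughly an 18–28% chance of at least one false positive for the ten tests as written (15–23% for seven)

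*Combined protocol and SAP*

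**What the plan says.** SAP section 2.2 sets out the between-arm analysis under "Comparison between groups (day 7 and day 14". The independent t-test is introduced with the words "This test was used to determine significant differences between the oral lumbrokinase DLBS1033 group and the betahistine group for", and five means follow: DHI, VSS-SF, TNF-α, IL-1β and VCAM-1.

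The next step depends on those results: "Given the significant statistical differences found with the independent T-test" is the stated reason for the repeated ANOVA of symptom improvement time. The only multiple-comparison procedure named is in the last line: "Tukey B post-hoc test was used to compare the mean scores/levels between groups".

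Nothing elsewhere ranks the outcomes. Section 1.1 opens with "The research aims to determine the differences in" and lists five objectives of equal standing. Section 1.2 gives "Dependent variables: inflammation level, quality of life, time to improvement of dizziness symptoms in BPPV patients", also unranked. The nearest thing to a significance level is "with a 95% confidence interval (CI) and 5% confidence limits" in the sample size paragraph of section 1.2, and that describes the sample size formula, not the tests.

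**The concern.** The t-tests are worded as the means of establishing differences between the arms, and significance in them is the gateway to further analysis. With several tests, no primary one among them and no adjustment, the chance that at least one is significant when the treatments do not differ exceeds the nominal level of a single test. A reader shown one or two significant results could not tell how surprising they are without knowing how many tests were run and at what level. In a trial of about 40 patients, a claim that lumbrokinase differs from betahistine could rest on such a result.

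**Working it through.** The plan states no error rate for these tests, so there is no figure of its own to reproduce.

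**Inputs from the documents**
- Five outcomes and two days (SAP 2.2): 5 × 2 = 10 tests as written.
- No section says on which days blood was drawn. If the three biomarkers were compared on one day only, the count is 2 × 2 + 3 × 1 = 7.
- Section 1.2 says "the calculation resulted in a minimum sample of 40 patients". Balanced groups were intended, so 20 per arm.

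**Assumptions, because the documents are silent**
- Two-sided 5% per test.
- No true difference on any outcome.
- Correlations between outcomes/between days of 0.5/0.8 (moderate) and 0.8/0.9 (high). For different outcomes on different days the correlation is the product of the two.

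**Independent tests (upper bound)**
- Ten tests: 1 − 0.95^10 = 0.401.
- Seven tests: 1 − 0.95^7 = 0.302.
- One outcome over two days: 1 − 0.95^2 = 0.0975.

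**Correlated tests** (simulated t-tests, 20 per arm, 40,000 runs)

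| Tests counted together | Independent | 0.5/0.8 | 0.8/0.9 |
|---|---|---|---|
| Ten (all outcomes, both days) | 40% | 28% | 18% |
| Seven (biomarkers on one day) | 30% | 23% | 15% |
| Two (one outcome, both days) | 10% | 8% | 7% |
| Holm over all ten, or all seven | 5% or less | 5% or less | 5% or less |

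The ten-test figure at 0.8/0.9 is not sensitive to the details. It is 17.7% with 20 per arm and 17.8% with 22 per arm. It is about 17% if different outcomes on different days are correlated at 0.8 instead of 0.8 × 0.9 = 0.72.

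**Does Tukey B supply the missing control?** With two arms there is one pair to compare. At 38 degrees of freedom the Tukey critical value is 2.8629/√2 = 2.0244, which equals t(0.975, 38) = 2.0244, so between two arms it is the same test. If it compares time points, it does not bear on the between-arm tests. If it compares arm-by-day means within one outcome, it gives some control over the two days but none over the five outcomes. In every case the separate t-tests stay unadjusted.

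**Cost of Holm, 20 per arm.** A difference of 0.91 SD is detected with 80% power at 0.05. Holm's first step over ten tests uses 0.05/10 = 0.005. Power at 0.91 SD is then 47%, and the difference detectable with 80% power rises to 1.22 SD. Later steps are less strict: if all ten comparisons truly differed by 0.91 SD, average power per test under Holm would be about 57–59%.

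**The case against.** The strongest reply is that the ten-test family is the reviewer's construction. Section 1.1 lists separate objectives, and nothing says the treatment succeeds if any one test is positive. Whether distinct, separately reported objectives need joint error control is debatable. This stands in part: on that reading the multiplicity is only the two days, and the rate is about 7–10% per outcome. That is milder but still above 5%, and the plan does not say that this is the reading it intends.

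Three stronger inferences are tempting, and the documents do not support them:
- *That the false-positive rate is 40%.* This requires independent tests, which is unrealistic when the same patients are measured on both days. It is an upper bound.
- *That exactly ten tests were run.* The heading in SAP 2.2 implies ten, but no section schedules blood sampling on both days. Section 1.4 mentions an allowance for each blood examination visit without saying which visits those are.
- *That the reported differences are false positives.* All the rates assume no outcome differs. SAP 2.2 refers to differences found without saying which or how many, so the effect on the actual conclusions cannot be judged from these documents.

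The cost to power is also a fair objection to making adjusted significance the only thing reported. It does not argue against showing adjusted results beside unadjusted ones.

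**Conclusion.** The concern holds, and it is more than a missing detail: following SAP 2.2 as written inflates the chance of a spurious between-arm finding, and no part of the plan offsets this. The realistic size is about 18–28% for ten tests or 15–23% for seven, and 7–10% per outcome on the mildest reading of the objectives. The existence of the problem rests on the text. Its size rests on an assumed 5% two-sided level, 20 per arm, no true difference and assumed correlations, none of which the plan states for these tests.

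**What to change.** In the report:
- State the significance level and the number of between-arm t-tests actually performed.
- Give Holm-adjusted p-values over all of those tests beside the unadjusted ones, labelled post hoc.
- Describe any comparison significant only before adjustment as exploratory, not as an established difference between the arms.
- Label 95% confidence intervals as unadjusted.
- Say which means Tukey B compared, and do not present it as multiplicity control.

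Use one family, namely all between-arm t-tests performed. SAP 2.2 is written in the past tense and already refers to differences found. Choosing a primary outcome, a primary day or a narrower family now would be a choice made with the results known.

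The work is a short recalculation from existing p-values and some rewording, with no new data. The price is power: at Holm's first step over ten tests it falls from 80% to 47% at 0.91 SD. That is the worst case for a step-down method, and it is the reason to keep the unadjusted results in the report.

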1.2 Design and Methods

- Type of research: This study is a clinical trial with a double-blind randomized controlled trial design.
- Place and time of research: The study was conducted at the neurology polyclinic of [name] General Hospital, Surakarta. Data collection began after obtaining ethics committee approval and continued until the required sample size was met, from April to August 2024.
- Research population: The actual research population consists of patients at the neurology polyclinic of [name] General Hospital, Surakarta, who met the inclusion and exclusion criteria.
- Research subjects: Subject selection was carried out using purposive sampling.
 - Inclusion criteria: BPPV patients at the neurology polyclinic of [name] General Hospital, aged 18-65 years, diagnosed by a neurologist or neurology polyclinic resident based on a history of worsening vertigo, nausea, vomiting, and imbalance with head movements, and findings of torsional nystagmus with latency, fatigability, and duration less than 60 seconds on Dix-

Hallpike maneuver; able to speak, read, and write Indonesian; and willing to cooperate as research subjects by signing the informed consent form.

- Exclusion criteria: Pregnant and breastfeeding patients; patients with neurological deficits indicative of central vertigo based on anamnesis and physical examination; patients with a history of ear infection, hearing impairment, tinnitus, and head trauma; patients with thyroid disorders, diabetes mellitus, genu osteoarthritis, history of neoplasm, history of heart disease and hypertension, history of ear/mastoid surgery, and currently experiencing other inflammatory and infectious conditions; patients with cognitive impairment based on attention and memory examination; patients participating in other clinical studies within 30 days before screening.
- Drop-out criteria: Patients who could not complete the entire research procedure; patients who did not follow procedures properly; patients who did not complete the DHI and VSS-SF questionnaires after receiving therapy.

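### Three objectives concern the between-arm difference in biomarker decrease, but the SAP tests only levels at day 7 and day 14, with no reference to baseline

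*Combined protocol and SAP*

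**What the plan says.** Section 1.1 (Objectives) sets three biomarker objectives in the same form, for example "Decrease in VCAM-1 levels between BPPV patients receiving oral lumbrokinase DLBS1033 therapy and those receiving betahistine therapy". The quality-of-life objective is not worded as a decrease: "Quality of life between BPPV patients receiving oral lumbrokinase DLBS1033 therapy and those receiving betahistine therapy".

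Section 2.2 (Specific Statistical Methods) compares the arms under "Comparison between groups (day 7 and day 14" by independent t-tests of mean DHI, VSS-SF, TNF-alpha, IL-1 beta and VCAM-1. It names no change score, baseline covariate or pre-treatment time point. Two further items follow:

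- A repeated ANOVA, introduced by "Given the significant statistical differences found with the independent T-test" and directed at time to symptom improvement in patients on lumbrokinase.
- A post-hoc step: "Tukey B post-hoc test was used to compare the mean scores/levels between groups".

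On blood sampling, section 1.4 mentions an allowance "per visit for blood examination", but no section schedules a draw before the first dose. On size, section 1.2 states that "the calculation resulted in a minimum sample of 40 patients", and that data collection "continued until the required sample size was met, from April to August 2024".

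**The concern.** A decrease is a change from a starting value. The SAP specifies no analysis that refers to a starting value, so the quantity named in three of the five objectives is not among the specified results. A reader would learn whether the arms differed at day 7 or day 14, but not from any specified analysis how far each biomarker fell in each arm, or whether the arms began at the same place.

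With about 20 patients per arm, randomisation leaves room for a noticeable chance gap at baseline. A raw comparison of later levels carries part of that gap into the estimate. It also leaves unused the precision that a patient's own baseline value can supply, in a trial that can detect only large differences.

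**Working it through.** **Does any other method fill the gap?** The repeated ANOVA is described for symptom improvement time within one treatment. Tukey B refers to scores and levels, so it may reach the biomarkers, but it names neither baseline nor change. Neither is specified as a between-arm contrast in decrease.

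**Is the planned t-test biased?** No. Randomisation gives both arms the same expected baseline, so the expected difference in decrease equals the expected difference in level with the sign reversed.

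**Inputs.** There are 40 patients (section 1.2), taken as stated; how that number was derived is a separate question. Equal arms of n = 20 are assumed, as no ratio is given. Data are taken as bivariate normal with equal SDs, and results are in SD units. The baseline to follow-up correlation ρ is not in the documents, so a range is shown. The plan gives no power or detectable difference for the biomarkers, so there is no such figure to reproduce.

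**Variance of the between-arm estimate, in units of 2/n:**

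- t-test of level: 1, with 38 df
- ANCOVA on baseline: (1 − ρ²)(2n − 3)/(2n − 4) = (1 − ρ²)(37/36), with 37 df
- t-test of decrease: 2(1 − ρ), with 38 df

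The 95% CI half-width is t × √(variance × 2/20). For the t-test of level this is 2.024 × 0.316 = 0.640. For ANCOVA at ρ = 0.5 it is 2.026 × √(0.1 × 0.75 × 1.0278) = 0.563. The detectable differences below are solved from the noncentral t distribution (80% power, two-sided 5%).

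| ρ | t-test of level | ANCOVA | t-test of decrease | ANCOVA CI half-width (level: 0.64) |
|---|---|---|---|---|
| 0.1 | 0.91 | 0.92 | 1.22 | 0.65 |
| 0.2 | 0.91 | 0.90 | 1.15 | 0.64 |
| 0.3 | 0.91 | 0.88 | 1.08 | 0.62 |
| 0.5 | 0.91 | 0.80 | 0.91 | 0.56 |
| 0.7 | 0.91 | 0.66 | 0.70 | 0.46 |

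**Break-even.** Setting (1 − ρ²)(37/36) = 1 gives ρ = √(1/37) = 0.164. Allowing for the lost degree of freedom gives about 0.17. At ρ = 0 the cost of ANCOVA is 37/36, about 3% in variance.

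**Chance imbalance.** The SD of the baseline mean difference is √(2/20) = 0.316. A gap above 0.5 SD in either direction has probability 2 × [1 − Φ(0.5/0.316)] = 0.114 per outcome, or 0.057 on the adverse side.

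- No true effect, gap above 0.5 SD: simulated trials give rejection rates for the raw t-test of about 8%, 14% and 22% at ρ = 0.3, 0.5 and 0.7, against about 5% for ANCOVA. Over all trials both hold 5%.
- True effect 0.7 SD, adverse gap above 0.5 SD: the average gap is 0.316 × φ(1.58)/[1 − Φ(1.58)] = 0.635 SD. The raw estimate therefore averages 0.7 − 0.635ρ, which is 0.51, 0.38 and 0.26 SD. ANCOVA averages 0.70. The raw sign is wrong in about 5%, 9% and 14% of these trials, and significantly wrong in under 0.1%.

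**Does ANCOVA answer the objective as worded?** Yes. If Y = a + τ·arm + βX, then X − Y = −a − τ·arm + (1 − β)X. The arm coefficient is the same apart from sign, whether level or decrease is the outcome.

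**The case against.** The strongest reply is that little inferential harm follows. The planned test is valid, targets the same expected effect and holds its error rate over all trials. Testing levels is also no worse than a literal t-test of the decrease unless ρ exceeds 0.5, so part of this point is a preference for efficiency. The gain rests on an unknown ρ: it is negligible at 0.2 and about 3% in detectable difference at 0.3, and becomes material nearer 0.5. The imbalance figures describe 11% or 6% of trials, and nothing shows that this trial was one of them. All of that stands, and it limits the weight of the point.

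Two further replies stand in part. The SAP lists tests and not descriptive tables, so mean changes might have been reported anyway; but none is specified. A pre-dose sample is implied rather than documented, so the remedy has to be conditional on it.

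The last reply is that six post hoc models, added after t-test results were known, bring multiplicity and a possible conflict of results. That is met by leaving the t-tests as the stated analysis and presenting the ANCOVA as supplementary estimates with intervals. None of these replies makes section 1.1 and section 2.2 agree.

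**Conclusion.** The mismatch is real and should be fixed. Three of five objectives name a quantity that no specified analysis estimates with reference to baseline. It does not invalidate the t-tests.

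Against a detectable difference of 0.91 SD, baseline adjustment would bring it to 0.88, 0.80 or 0.66 SD at ρ = 0.3, 0.5 or 0.7, with no gain below about 0.17. A chance baseline gap mainly distorts the size of the raw estimate and rarely reverses it. These figures assume 20 completers per arm, normal data and the stated range of ρ. Confidence is high on the mismatch; the size of the precision gain depends on ρ, and the feasibility of the remedy on whether pre-treatment samples were taken.

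**What to change.** State in the protocol whether biomarkers were measured before the first dose. If they were, keep the t-tests and add to section 2.2:

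> Post hoc supplementary analysis. For each of IL-1 beta, TNF-alpha and VCAM-1, an ANCOVA of the day-14 value, and separately of the day-7 value, on arm and the patient's own pre-treatment value. The adjusted between-arm difference with 95% CI is reported as the difference in decrease, together with the baseline mean and the mean change (SD) in each arm.

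Mean change serves as description and ANCOVA as the comparison, because a t-test of the change loses precision against the planned test when ρ is below 0.5. The post hoc label is needed because data collection has ended and section 2.2 already cites t-test results. DHI and VSS-SF may be handled in the same way for precision. Adjustment for age, body mass index and gender is at most an optional sensitivity model; leaving them out is not an error under randomisation.

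If no pre-treatment sample exists, reword the three objectives as levels at day 7 and day 14.

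The cost is one error degree of freedom (38 to 37), a re-run in SPSS and a few lines of text. No new data are needed if the baseline was collected, but the ANCOVA cannot be presented as pre-specified.
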